Appendix 5. Addition of New Key Secondary and Exploratory Outcomes

A5.1 Rationale for new Secondary and Exploratory Outcomes

Health-related quality of life data has been collected on participants in ACTIV 4c by use of the EuroQol 5 Dimension 5 Level (EQ-5D-5L) survey, administered at three timepoints following randomization into the study: Day 2 (within the first few days of starting study drug), Day 30 (time of completion of study drug), and Day 90 (60 days after completion of study drug). The EQ-5D survey consists of five questions that cover the following domains: mobility, self-care, usual activities, pain/discomfort, and anxiety/depression. The response to each question is collected as a 5-level ordinal scale, spanning scores of 1 (no problems, or best outcome), 2 (slight problems), 3 (moderate problems), 4 (severe problems) and 5 (extreme problems, or worst outcome). The rationale for collecting these quality of life data was driven by early reports describing a significant subset of patients with COVID-19 who had a prolonged course with persistent symptoms of fatigue, dyspnea, and other problems, lasting for months and longer after the acute illness.

An analysis of the EQ-5D data was not included in the Master Protocol, since study leadership had not anticipated that anticoagulant therapy would have a significant impact on quality of life. A post-hoc analysis of EQ-5D data collected in ACTIV 4a, however, comparing prophylactic-dose with therapeutic-dose anticoagulation in hospitalized patients with COVID-19 in the non-ICU setting, observed that patients randomized to therapeutic anticoagulation had less moderate-to-extreme impairment scores in four of the five EQ-5D domains at 90 days after hospital discharge. This difference was statistically significant in the self-care domain, with an improvement from 8.4% to 2.9% of participants having moderate-to-extreme impairment scores with therapeutic anticoagulation, for an odds ratio (adjusted for age, co-morbidities and pre-hospitalization status) of 0.26 (95% CI, 0.08-0.83) and a p-value of 0.016 ([name] and [name], personal communication). This preliminary observation that anticoagulant therapy could impact quality of life in patients with COVID-19 resulted in the decision by the ACTIV 4c leadership team to include an analysis of the collected EQ-5D data in two new secondary objectives and one new exploratory objective.

A5.2 New Secondary Objectives

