2	Does Apixaban improve the composite of QOL and mortality at 30 days after discharge?	Key Secondary Objective of the Study / All Randomized Participants	Composite endpoint of mortality and EQ5D index at Day 30. All mortality events will be considered worse than any possible EQ5D response [QOL&M30]	The expected rate of missing data for the EQ5D endpoint is expected to be approximately 20%. The odds ratio will be estimated using maximum likelihood methods which yield valid estimators under the MAR (or MCAR) assumptions.	The odds ratio from a proportional odds model with the EQ5D index and mortality endpoint as the response variable. Values greater than 1.0 will favor the Apixaban arm.
3	Does Apixaban improve the composite of QOL and mortality at 90 days after discharge?	Key Secondary Objective of the Study / All Randomized Participants	Composite endpoint of mortality and EQ5D index at Day 90. All mortality events will be considered worse than any possible EQ5D response [QOL&M90]	The expected rate of missing data for the EQ5D endpoint is expected to be approximately 20%. The odds ratio will be estimated using maximum likelihood methods which yield valid estimators under the MAR (or MCAR) assumptions.	The odds ratio from a proportional odds model with the EQ5D index and mortality endpoint as the response variable. Values greater than 1.0 will favor the Apixaban arm.
4	Does Apixaban reduce the rate of venous	Key Secondary Objective of	Composite endpoint of venous thromboembolic	Inter-current events will be death and	The difference in the

	thromboembolic outcomes during 30 days after discharge?	the Study / All Randomized Participants	events, including symptomatic DVT of the upper or lower extremities, symptomatic and/or clinically relevant PE, and other symptomatic venous thrombosis, including cerebral sinus and splanchnic vein thrombosis at day 30 [CEVTE30]	patient drop-out. Patients who died without an intercurrent event will be censored. The drop-out is expected to be less than 5% and un-related to treatment and their data up to the time of drop-out will be used in the event determination*	proportion of CEVTE30 between the Apixaban arm and the placebo arm. A negative value will favor the Apixaban arm.

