7	Does Apixaban reduce the rate of venous and arterial thromboembolic outcomes, and all-cause mortality during 90 days after discharge?	Key Secondary Objective of the Study / All Randomized Participants	Composite endpoint of venous and arterial thrombotic complications—including new, symptomatic proximal, or distal DVT of the upper or lower extremities, PE, and new thrombosis of other veins (including cerebral sinus and splanchnic veins), ischemic stroke, myocardial infarction, other arterial thromboembolism (e.g., mesenteric or acute limb ischemia), and all-cause mortality by day 90 [CE90]	The only inter-current event will be patient drop-out. The drop-out is expected to be less than 5% and un-related to treatment and their data up to the time of drop-out will be used in the event determination*	The difference in the proportion of CE90 between the Apixaban arm and the placebo arm. A negative value will favor the Apixaban arm.

\*See the sensitivity analysis (Section 4.2)

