#### 4.3 ANALYSIS OF THE SECONDARY EFFICACY ENDPOINT(S)

Six secondary outcomes are of interest in this trial. We will use a fallback method to control for type I error (see page 30 of the Food and Drug Administration guidance on multiple endpoints in clinical trials; <https://www.fda.gov/regulatory-information/search-fda-guidance-documents/multiple-endpoints-clinical-trials-guidance-industry> ). More specifically, these secondary outcomes will only be formally tested if the primary hypothesis was rejected at level alpha=0.05. If the study stops without the CE30 test statistic crossing the 'efficacy boundary' or 'futility boundary' (i.e. not enough primary endpoint events), the key secondary endpoints will be evaluated and summarized using point estimates and associated 95% confidence intervals (without p-values).

The ordering of the secondary endpoints is as follows:

- 1) Composite endpoint of mortality and EQ5D index at Day 30 (QOL&M30)
- 2) Composite endpoint of mortality and EQ5D index at Day 90 (QOL&M90)
- 3) Primary endpoint at 45 days (CE45)

- 4) Primary endpoint at 90 days (CE90)
- 5) Venous events at 30 days (CEVTE30)
- 6) Arterial events at 30 days (CEATE30)

Using a fallback method the 0.05 type I error rate would be split as follows – 0.025, 0.005, 0.005, 0.005, 0.005, and 0.005. If QOL&M30 was statistically significant then QOL&M90 would be tested at  $0.03 = 0.025 + 0.005$ . On the other hand, if QOL&M30 was NOT statistically significant then QOL&M90 would be tested at 0.005. The process would continue until all 6 secondary endpoints were tested. If the study does not accumulate enough CE30 events, it is expected that there would be limited information for secondary endpoints 3-6.

Statistical methods for testing the QOL&M30 and QOL&M90 endpoints will be based on a proportional odds model. The covariates in the model will include the participant's age (restricted cubic spline with 3 knots), sex, D-dimer (normal or abnormal), BMI (restricted cubic spline with 3 knots), antiplatelet usage (yes/no - at enrollment), WHO severity score (<five vs.  $\geq$ five), and the randomized treatment. The results of these models will be summarized using an odds ratio and associated 95% confidence interval.

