Secondary analyses of the QOL&M30 and QOL&M90 endpoints will use a multiple imputation approach. 20 datasets will be imputed using predictive mean matching and the above covariates plus the Day 2 and Day 90 EQ5D index scores. The model estimates will be combined using Rubin's rules to obtain the estimated odds ratio and 95% confidence interval.

Statistical methods for testing the secondary endpoints 3-6 listed above will follow the same procedures used for the primary endpoint described in Section 4.2 above. Except that for the CEVTE30 and CEATE30 events, an additional sensitivity analysis will be conducted by combining death from any causes to each one of the events separately.

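### For Day 90 quality of life, the imputation list names the score being imputed and omits the Day 30 score

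*SAP*

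**What the plan says.** Protocol A5.1 states that the EQ-5D is "administered at three timepoints following randomization into the study: Day 2 (within the first few days of starting study drug), Day 30" and Day 90, so a Day 30 score is collected. The estimand table in SAP 3.2 says of each QOL endpoint that "The expected rate of missing data for the EQ5D endpoint is expected to be approximately 20" per cent, and relies on maximum likelihood under MAR or MCAR.

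The main analysis in SAP 4.3 is a proportional odds model. Its covariates are age, sex, D-dimer, BMI, antiplatelet use, WHO severity score and treatment. No other EQ5D visit enters it.

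SAP 4.3 then adds that "Secondary analyses of the QOL&M30 and QOL&M90 endpoints will use a multiple imputation approach", and gives one specification for both: "20 datasets will be imputed using predictive mean matching and the above covariates plus the Day 2 and Day 90 EQ5D index scores". Protocol A5.5 carries the same sentence.

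For the remaining secondary endpoints, SAP 4.3 says that methods for "testing the secondary endpoints 3-6 listed above will follow the same procedures used for the primary endpoint" in Section 4.2. That section contains the tipping-point analysis. In the estimand table, the footnote pointing to the Section 4.2 sensitivity analysis is marked on rows 1 and 4-7, but not on rows 2 and 3, the two QOL rows.

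**The concern.** Day 2 and Day 90 are the right companions for a missing Day 30 score. For a missing Day 90 score, one named predictor is the missing value itself, and the closest earlier measurement is not named. What remains is Day 2 plus the baseline covariates and treatment.

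No other missing-data check is stated for the two QOL endpoints, and the main model ignores the other EQ5D visits. The imputation is therefore the only stated QOL analysis that uses the repeated scores. A weak Day 90 model recovers less of the lost information. It also removes less bias if people with a poor Day 30 score drop out of the Day 90 assessment to a different degree in the two arms.

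This matters most if the study stops without crossing a boundary. SAP 4.3 then has the key secondary endpoints reported as estimates with 95% confidence intervals and no p-values, and it expects limited information on endpoints 3-6. The QOL estimates would be the more informative ones.

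**Working it through.** **The plan's own figures.** The fallback split is 0.025 + 5 × 0.005 = 0.05, and QOL&M90 is tested at 0.025 + 0.005 = 0.03, or at 0.005. Both agree with the text. At 20% missing and 2,660 per arm, 0.20 × 2,660 = 532 EQ5D scores per arm would be missing. The documents give no correlations between visits and no missingness mechanism, so the figures below rest on assumed ranges.

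**Precision (no arm difference needed, Day 30 observed).** Let a, b and c be the Day 2-30, Day 2-90 and Day 30-90 correlations.

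- Day 2 only: R² = b².
- Day 2 + Day 30: R² = (b² + c² − 2abc)/(1 − a²). For 0.6/0.4/0.7 this is (0.16 + 0.49 − 0.336)/0.64 = 0.49.
- With 80% observed, the variance relative to full data is R² + (1 − R²)/0.8, against 1.25 for complete cases. The share of lost information recovered equals R².
- Fall in SE = 1 − √(factor with both / factor with Day 2 only).

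| a / b / c | R², Day 2 only | R², Day 2 + 30 | Factor, Day 2 only | Factor, Day 2 + 30 | Fall in SE |
|---|---|---|---|---|---|
| 0.6 / 0.4 / 0.7 | 0.16 | 0.49 | 1.210 | 1.127 | 3.5% |
| 0.6 / 0.5 / 0.6 | 0.25 | 0.39 | 1.188 | 1.152 | 1.5% |
| 0.4 / 0.3 / 0.5 | 0.09 | 0.26 | 1.228 | 1.185 | 1.8% |

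**Bias (simulation, true odds ratio 1.00).** Set-up: 200 replicates with 2,530 per arm; 4% deaths, known and ranked worst; EQ5D in ten ordered levels above death; 20% of survivors missing Day 90, with log-odds of missing linear in Day 30. Each method fits a proportional odds model with treatment. The imputations use predictive mean matching (5 imputations, Rubin's rules), chained where Day 30 is included. Baseline covariates are left out. The SE of the log odds ratio is about 0.054, and the Monte Carlo SE of its mean about 0.004. Ranges cover the three correlation sets. The last two columns are for 50% or 80% of those missing Day 90 also lacking Day 30.

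| Odds of missing per SD worse Day 30, by arm | Complete case | Day 2 only | Day 2 + 30, Day 30 observed | 50% lack Day 30 | 80% lack Day 30 |
|---|---|---|---|---|---|
| Same in both arms | 1.00 | 1.00 | 1.00 | 1.00 | 1.00 |
| ×1.5 vs ×2.5 | 1.06-1.09 | 1.04-1.06 | 1.00 | 1.02-1.03 | 1.03-1.04 |
| None vs ×2 | 1.10-1.15 | 1.06-1.10 | 1.00 | 1.03-1.04 | 1.05-1.07 |

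On the SE scale, the Day 2 only bias is ln(1.04)/0.054 = 0.7 to ln(1.06)/0.054 = 1.1 in the modest case, and 1.1 to ln(1.10)/0.054 = 1.8 in the strong case.

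**Second simulation, different outcome model.** This used a normal score analysed as a mean difference, 1,200 participants in total, about 20% missing, 20 imputations, and correlations of 0.5-0.6 / 0.4-0.5 / 0.6-0.8. When a poor Day 30 score drove missingness in one arm only, the bias was 0.075-0.098 SD with Day 2 only and 0.000-0.003 SD with Day 30 added. With missingness unrelated to the scores there was no material bias, and the fraction of missing information fell from 0.15-0.17 to 0.08-0.13.

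**The case against.** The sentence may describe one imputation run that fills all visits together. A chained model would then use Day 30 for Day 90 as a matter of course. Read literally for QOL&M90, the list asks for Day 90 to be predicted from itself; that cannot be run, so the programmer would have to resolve it. This is possible, but neither document mentions a joint or chained model, and a pre-specified analysis should not depend on an unwritten choice.

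Several limits on the size do stand:

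- The imputation is a secondary analysis. The fallback test of QOL&M90 uses the main model and does not change.
- The bias needs an arm difference in how missingness depends on Day 30. The trial is double-blind and placebo-controlled, and nothing in the documents points to such a difference.
- The calculations omit the baseline covariates that the plan does include. So far as these predict EQ5D, the written plan recovers more, and leaves less bias, than the Day 2 only figures show.
- The gain shrinks when people who miss Day 90 also miss Day 30. The documents give no rate for this.
- An early stop enlarges the SE. At an assumed 600 per arm it is about 0.054 × √(2,530/600) = 0.11, and ln(1.06) = 0.058 is about half of that.
- Corrected imputation still assumes MAR, so the QOL endpoints would still have no check against data missing not at random.

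**Conclusion.** The concern holds. The predictor list is wrong for QOL&M90 as written, in both documents, and nothing elsewhere in either corrects it. If followed literally, it makes the only stated missing-data check on that endpoint weaker than the collected data allow.

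The precision loss is small, but it needs no differential mechanism. The bias is conditional: none if missingness depends on Day 30 equally in both arms; an odds ratio of 1.04-1.06 (modest arm difference) or 1.06-1.10 (strong) in place of 1.00 with Day 2 alone. Adding Day 30 removes this fully only where Day 30 is observed. These sizes rest on assumed correlations, an assumed missingness mechanism, 2,530 per arm and no baseline covariates; they show direction and plausible order, not a forecast. The primary endpoint and the alpha allocation are not touched. The correction should be made, mainly because a wrong rule is stated and the right one is nearly free.

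**What to change.** In SAP 4.3 and Protocol A5.5, state the predictors for each endpoint:

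- Missing Day 30 EQ5D: the model covariates (including treatment), Day 2 and Day 90.
- Missing Day 90 EQ5D: the model covariates (including treatment), Day 2 and Day 30.

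Alternatively, state that Days 2, 30 and 90 are imputed jointly by chained equations with those covariates, which also covers participants missing both Day 30 and Day 90. In either case, say that EQ5D is imputed for survivors only and that known deaths are then ranked worst, as the endpoint already specifies.

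The cost is one sentence in each document and trivial programming. It uses data already collected and changes neither the main model nor the alpha split.

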#### 4.4 SAFETY ANALYSES

The rates of safety outcomes listed in section 3.0.3 (e.g., ISTH major bleeding and the rate of ISTH CRNMB) during the 30-day treatment period and during the additional 60-day safety follow-up period between the two arms will be compared. The proportion of patients in each assigned treatment group who experience each safety event, the relative risk, and the absolute risk difference will be calculated from the observed data, and confidence intervals will be calculated. Analyses of the bleeding outcomes that occur during the full 90-day follow-up period (i.e., 30-day treatment period plus the 60-day safety follow-up) will also be conducted as part of the trial safety analyses. This analysis will be done for mITT population only (participants who had at least one dose of the drugs).

#### 4.5 EXPLORATORY ENDPOINTS AND ANALYSES

Exploratory endpoints for this trial include the following.

1. All-cause mortality at day 30 following discharge from the hospital
2. All-cause re-hospitalization at day 90 following discharge from the hospital

For each of the above endpoints, the proportion achieving endpoints and the corresponding 95% confidence intervals will be presented by the treatment group using the Wald method and Clopper-Pearson exact intervals (Clopper and Pearson, 1934). Also, relative risk and the absolute risk differences with corresponding 95% confidence intervals will be estimated and presented.

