There are also an increasing number of reports describing patients with COVID-19 who develop thromboembolic events in the outpatient setting. Two recent studies described patients with COVID-19 being evaluated for progressive respiratory symptoms in the Emergency Department, finding PE by CT angiography in 18% to 23% of patients (12, 13). Previously undiagnosed DVT and PE have also been identified by autopsy in patients dying at home or in a nursing home (14), and a case report described an asymptomatic individual with COVID-19 who presented with sudden death due

to massive PE (15). Whether VTE rates are increased in non-hospitalized patients with COVID-19 is unknown, however.

Similarly, limited data exist concerning the risk of thromboembolic complications for patients with COVID-19 in the post-discharge/convalescence setting. One study noted that out of 1,368 patients discharged following a hospitalization related to COVID-19, 61 patients (4.4%) were re-admitted, 10 for a thrombotic event in venous or arterial territory (16).

Extended thromboprophylaxis following hospitalization in non-COVID-19 patients

Multiple studies have documented that a recent hospitalization is associated with an increased risk for VTE in the post-discharge setting. This increased risk for PE and DVT remains markedly elevated for at least the first month after hospital discharge (17). Although several trials have investigated whether an extended course of thromboprophylaxis with an anticoagulant can decrease this increased risk for VTE, none have shown a substantial improvement in the VTE rate (Table 1). There are unique aspects to each of the studies that may have contributed to the observed outcomes, however.

Table 1. Clinical trials investigating thromboprophylaxis in patients hospitalized for acute medical illness.*

| Clinical Trial | Arms | Efficacy outcome(s) | Event rate for anticoagulant | Event rate for placebo | Comparisons [†] (95% CI) |
|----------------|--|--|------------------------------|------------------------|--------------------------------------|
| EXCLAIM (18) | (1) Enoxaparin vs. (2) Placebo | Symptomatic VTE at 28 d | 0.2% | 1.0% | -0.75 (-1.19 to -0.32) |
| ADOPT (19) | (1) Apixaban (extended course) vs. (2) Enoxaparin (short course) | Total VTE [‡] or VTE-related death | 2.71% | 3.06% | 0.87 (0.62-1.23) |

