**Exploratory Objectives:**

- Exploratory Objective 1: To compare the effects of treatment beginning at the time of discharge from the hospital with either Arm A or Arm B on the incidence of all-cause rehospitalization for up to 90 days after randomization.
- Exploratory Objective 2: To compare the effects of treatment beginning at the time of discharge from the hospital with either Arm A or Arm B on the incidence of all-cause mortality for up to 30 days after randomization.
- Exploratory Objective 3: To compare the effects of treatment beginning at the time of discharge from the hospital with either Arm A or Arm B on the individual domains of EQ5D and the EQ5D visual analog scale for 30 and 90 days after randomization.

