### 3.5 POWER AND SAMPLE SIZE

The primary analysis for this randomized trial will be an intention-to-treat comparison of a composite endpoint (CE) of venous thromboembolic events, including new, symptomatic proximal or distal deep vein thrombosis affecting the upper and/or lower extremities, pulmonary embolism, or thrombosis of other veins (e.g., cerebral sinus veins, splanchnic veins); arterial thromboembolic events, including new ischemic stroke, myocardial infarction, mesenteric or peripheral arterial thromboembolism; and all-cause mortality for up to 30 days after randomization across the intervention arms. This binary primary endpoint was used to power the study.

The MARINER trial reported a 2% event rate for a combined outcome of VTE, MI, CVA, or CV deaths in the placebo group (Spyropoulos, 2018). These rates are expected to be higher in COVID-19 patients who are discharged from the hospital. Recent information from patients discharged alive from the University of Pittsburgh Medical Center suggests that the 30-day mortality rate in this population could be as high as 4%. To be conservative, 4% was used as the expected CE rate of events for the no anticoagulant arm. An effect size of 35% percent risk reduction (risk ratio = 0.65) in the anticoagulant group compared to the no anticoagulant group was used to calculate the expected sample size for the study.

The analysis will use a group-sequential two-sample two-sided Z-test for proportions with pooled standard deviation to test the primary hypothesis at overall significance two-sided level alpha = 0.05. Four equally spaced interim analyses and one final analysis will use O'Brien-Fleming alpha spending boundaries for efficacy and the Hwang-Shih-DeCani boundaries for the futility reviews (O'Brien and Fleming, 1979; Hwang, Shih, and De Cani, 1990). In order to ensure an 80% power to detect a CE rate reduction of 35% through anticoagulation use, the study needs to enroll at least 2,530 participants per arm. Since the primary outcome is observed within 30 days of follow-up, the loss to follow-up and withdrawal of consent rates should be low, and it is estimated that CE will be missing on a maximum of 5% of the participants. Therefore, the sample size required for this study will be approximately 2,660 per

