### 3.11 SUBJECT DISPOSITION

The disposition of subjects (number randomized, number who received any amount of the randomly assigned treatment, number completing study drug administration, number who withdrew consent or discontinued from study drug early, and number lost to follow-up, and number who completed the trial) will be summarized by treatment group. The number of subjects screened for inclusion and a breakdown of reasons for exclusion will be summarized. The timing and reasons for early discontinuation of study drug and/or withdrawal from the study will be summarized by treatment group. For the calculation of percentages, subjects who die will not be included in the denominators for visits/assessments beyond their death. Treatment compliance (e.g., number of subjects with missed doses) will be summarized by treatment group. A subject listing of analysis population eligibilities will be generated. A listing of all subjects discontinued from the study after enrollment, broken down by site and treatment group will be provided. The listing will include the reason for discontinuation, treatment group, duration of treatment, and whether or not the blind was broken. Also, for subjects who discontinued from the study after enrollment, a listing of adverse events will be provided. Subject-specific protocol deviations will be summarized by the reason for the deviation, the deviation category, treatment group, disease severity, and (separately) site for all subjects. All subject-specific protocol deviations and non-subject-specific protocol deviations will be included in listings.

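### The Day 90 re-hospitalisation comparison in SAP 4.5 makes no provision for death, so a survival benefit could appear as a modest excess of readmissions

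*SAP*

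**What the plan says.** - SAP 4.5 names two exploratory endpoints: all-cause mortality at Day 30 and "All-cause re-hospitalization at day 90 following discharge from the hospital". For each it plans the proportion per arm with Wald and Clopper-Pearson intervals, plus relative risk and risk difference with intervals. It plans no hypothesis test and gives no rule for death before readmission.
- The estimand table in SAP 3.2 treats death as an intercurrent event for CEVTE30 and CEATE30. It has no row for re-hospitalisation.
- SAP 3.11, on subject disposition, says that "subjects who die will not be included in the denominators for visits/assessments beyond their death". It does not say whether this extends to SAP 4.5.
- Exploratory Objective 3 (SAP 2.0, Protocol A5.3) compares arms on the "individual domains of EQ5D and the EQ5D visual analog scale for 30 and 90 days after randomization". Protocol A5.5 refers the reader to the SAP for details, but SAP 3.2 and 4.5 do not list these measures and give no method for them.
- Elsewhere the plan does deal with death. For CEVTE30 and CEATE30, SAP 4.3 states that "an additional sensitivity analysis will be conducted by combining death from any causes to each one of the events separately". For the EQ5D index composites, the table in SAP 3.2 states: "All mortality events will be considered worse than any possible EQ5D response". CE90 includes all-cause mortality to Day 90.

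**The concern.** A participant who dies at home on Day 12 can never be readmitted. In a bare proportion that death is either scored as not readmitted, which is the favourable category, or dropped from the denominator. SAP 4.5 does not say which. Either way, an arm with fewer deaths has more people left who can be readmitted. If patients kept alive by apixaban are readmitted more often than average, the arm that saved them looks worse on readmission even when the drug has no other effect on it.

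The readmission result runs to Day 90, while the only mortality comparison listed on its own stops at Day 30. A reader of the re-hospitalisation row would therefore not see deaths on Days 31 to 90 next to it. What is at stake is how that row is read. No formal decision in the plan depends on it.

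**Working it through.** **The plan's own figure.** SAP 3.5 gives no calculation for exploratory endpoints, so its sample size serves only to set the precision. With 4.0% against 2.6%, two-sided alpha 0.05 and 80% power:

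n = [1.960 × √(2 × 0.033 × 0.967) + 0.842 × √(0.04 × 0.96 + 0.026 × 0.974)]² / 0.014² = 2,555 per arm (fixed design), against 2,530 stated. Allowing for 5% missing, 2,530 / 0.95 = 2,664, against about 2,660 stated. Both agree within about 1%, and I use 2,530 per arm below.

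**Inputs from the documents**
- Readmission: r = 61/1,368 = 4.46%. Protocol 1.1 reports that "61 patients (4.4%) were re-admitted, 10 for a thrombotic event in venous or arterial territory". No time window is given.
- Mortality: SAP 3.5 says that 30-day mortality could be as high as 4%, so this is an upper figure.
- Effect: risk ratio 0.65, which the plan assumes for the composite and not for death.

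**Assumptions**
- Placebo mortality before any readmission, m, is 1%, 2% or 4%.
- The full 0.65 applies to death.
- The drug has no other effect on readmission.
- A fraction q of the patients kept alive is readmitted.

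**Formulas, deaths counted as not readmitted.** Placebo = (1 − m) × r. Apixaban = (1 − m) × r + 0.35 × m × q. z = difference / √[pP(1 − pP)/2,530 + pA(1 − pA)/2,530].

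| m | q | Placebo | Apixaban | RR | z |
|---|---|---|---|---|---|
| 1% | 0.25 | 4.41% | 4.50% | 1.02 | 0.15 |
| 1% | 0.5 | 4.41% | 4.59% | 1.04 | 0.30 |
| 1% | 1 | 4.41% | 4.76% | 1.08 | 0.59 |
| 2% | 0.25 | 4.37% | 4.54% | 1.04 | 0.30 |
| 2% | 0.5 | 4.37% | 4.72% | 1.08 | 0.60 |
| 2% | 1 | 4.37% | 5.07% | 1.16 | 1.17 |
| 4% | 0.25 | 4.28% | 4.63% | 1.08 | 0.60 |
| 4% | 0.5 | 4.28% | 4.98% | 1.16 | 1.18 |
| 4% | 1 | 4.28% | 5.68% | 1.33 | 2.29 |

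If those spared are readmitted at about the average rate (q = 0.044), the RR is 1.00 to 1.01.

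**Deaths dropped instead.** At m = 4%, q = 0.5: placebo 4.281/0.96 = 4.46%, apixaban 4.981/0.974 = 5.11%, RR 1.15. The choice of denominator does not remove the lean.

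**A higher readmission rate.** If 90-day readmission were 10% (assumption), adding 0.7 or 1.4 points gives 10.7/10 = 1.07 or 11.4/10 = 1.14.

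**Fewer thrombotic readmissions.** 10/1,368 = 0.73%. Over the 96% who survive in either arm, a 35% reduction removes 0.96 × 0.73 × 0.35 = 0.25 points. At m = 4% the net excess is 0.35 − 0.25 = 0.10 points for q = 0.25 (RR 1.02) and 0.70 − 0.25 = 0.45 points for q = 0.5 (RR about 1.1).

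**Death or readmission, m = 4%.** Placebo 4.28 + 4 = 8.28%. Apixaban (readmissions + 2.6) = 6.94%, 7.23%, 7.58% and 8.28% for q = 0.044, 0.25, 0.5 and 1. The reversal disappears.

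**EQ5D domain, if analysed among survivors.** Take 8.4% impaired (a figure from another trial, Protocol A5.1), m = 4%, and 0.8 × 2,530 = 2,024 per arm before deaths, allowing for the 20% missing in the SAP 3.2 table. Apixaban = (0.96 × 0.084 + 0.014 × q)/0.974 = 8.6%, 9.0% and 9.7% for q = 0.25, 0.5 and 1, with z = 0.27, 0.66 and 1.44. Dead-or-impaired is 12.06% on placebo against 11.01%, 11.36% and 12.06%.

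**The case against.** The strongest reply has four parts.

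1. **Nothing is decided on this endpoint.** It is exploratory, sits outside the fallback procedure, and is reported with intervals and no test. This stands. CEVTE30 and CEATE30 carry alpha, so their fuller treatment of death is not in itself an inconsistency.
2. **Death to Day 90 is already analysed.** CE90 includes it and QOL&M90 ranks it worst. The DSMB tables in SAP Appendix 2 also have a mortality row by arm for all randomised participants. This largely stands, but none of these is a death-inclusive readmission result or a stand-alone 90-day mortality comparison in the final analysis.
3. **The large figures need stacked assumptions.** They put the whole composite effect on death, as if no primary event were a non-fatal VTE, stroke or MI. They take mortality at its upper figure and ignore prevented thrombotic readmissions. A death during a readmission already counts as a readmission, which shrinks the effect further. This stands. Preventing thrombotic readmissions masks the lean in the observed RR, however, and does not abolish it.
4. **Scoring a death as not readmitted is legitimate if the endpoint is readmission alone.** This also stands. The proportion can stay as it is, provided the rule is written down and death is shown with it.

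A reader might infer three stronger things. One is that the plan is likely to show significant harm from a life-saving drug. Expected z passes 1.96 only in the last row of the table. Another is that the patients spared are the sickest, which would justify a high q. No section says so, and Protocol 5.2 excludes life expectancy under 90 days. The third is that the plan chose a survivors-only analysis of the EQ5D domains and VAS. The SAP chose no analysis for them, so the gap is a missing method.

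**Conclusion.** The point holds as a matter of interpretation, and its size is modest. As written, SAP 4.5 lets a mortality benefit raise the apparent readmission rate on apixaban and does not place 90-day mortality beside that result.

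Under moderate assumptions the apparent relative risk is about 1.0 to 1.1. That covers placebo mortality of 1% to 2% with up to half of those spared readmitted, 4% with a quarter readmitted, and 4% with half readmitted once prevented thrombotic readmissions are counted. Without that allowance, 4% with half readmitted gives 1.16. About 1.3 requires 4% mortality, the full 35% effect on death and readmission of every patient spared.

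These are illustrations. The documents give no mortality effect, no q and no 90-day readmission rate. Neither the primary analysis nor the alpha-controlled secondary tests are affected.

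**What to change.** In SAP 4.5:

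1. State that all randomised participants stay in the re-hospitalisation denominator, with a death without readmission counted as not readmitted, and that the disposition rule in SAP 3.11 does not apply here.
2. Add re-hospitalisation or death by Day 90 as a supporting analysis, following the approach of SAP 4.3 for CEVTE30 and CEATE30.
3. Report 90-day all-cause mortality by arm beside both.
4. State a method for the EQ5D domains and VAS. Either label the results as among survivors and show them next to mortality and QOL&M30/QOL&M90, or add a supporting analysis that ranks death worst, as is already done for the EQ5D index.

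The cost is a few lines of text and some extra table rows. No new data are needed: deaths and re-hospitalisations are already adjudicated (SAP 3.4) and EQ5D is collected at Days 30 and 90 (Protocol A5.1). The downside is that the composite mixes death with readmission. If every patient spared were readmitted it would show no difference at all (8.28% in both arms above), so the components should also be shown separately.
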